15.4.4 Outcomes and objectives

Comprehensive flow-chart of the management of a patient presenting with, and treated for, suspected infection. The flow-chart will be used to inform the simulation logic during the software development process.

 - Hospitalised patients - collection of blood cultures for patients not previously suspected of being infected
- Flowchart exit points:
 - Completion of antimicrobial course of therapy (either on clinician decision that infection is unlikely, or completion of prescribed multi-day antimicrobial course)
 - Reporting of negative blood culture when infection suspected but empirical treatment not initiated
- Appropriate use of flowchart notation as described in Appendix 5 – Flowchart Design Principles, in particular:
 - Decision steps
 - Estimated time required for time-dependent events
 - Resource requirements, where applicable (e.g., staff resource, medications and equipment)
 - Re-entrant pathways (or loops) – e.g., as triggered when a patient clinically deteriorates

Flowchart construction will be adapted from a process modelling study of the ABCDE primary survey in trauma resuscitation (Lodemann et al., 2022). However, since our study is intended to be developed primarily as a DES model rather than an ABM one, additional notation is introduced to clarify which staff member is required for a particular step.

It is acknowledged that real patient management has high variability, and some events can be performed differently (by necessity, or by patient or staff choice), leading to the same outcome. The flowchart should capture the core events and decisions that guide the patient journey.

The study will take an iterative approach, whereby data from the sessions/meetings is collected, explored, and converted into a flowchart. At each step, the output of the qualitative analysis will be fed back to the participants and the process repeated (Figure 2).

[figure not shown]

Figure 2 - Iterative process of qualitative data collection and analysis

15.4.6 Data analysis

Meetings and focus group sessions will be recorded (with consent) and transcribed. Data will be analysed using [NVivo](#) to pick out key themes and themes that overlap between participants. This qualitative data will be used to construct a process flowchart as described in the previous sections. Flowcharts will be designed based with the intention of being informative and rigorous for model software development. To ensure consistency in notation, a set of design principles have been agreed and are described in Appendix 5 – Flowchart Design Principles. Specialist visualisation software – [Microsoft Visio](#) and [mermaid.js](#) – will be used to create easy to read flowcharts.

Once the final flowchart is agreed, the study team will proceed to code the simulation logic in an appropriate simulation modelling framework and language. The prototype model was constructed using the SimPy module within the Python programming language (“SimPy,” 2020). However, depending on the complexity of the final model, an alternative language or framework may be more appropriate. This will be discussed and explored within the study group meetings.

15.5 Sub-study 2 – Retrieval of retrospective routinely collected clinical data

15.5.1 Aim

Generate an anonymised individual-level dataset that will be used to calibrate the model's parameters.

15.5.2 Study setting

This retrospective routinely collected clinical data required for this sub-study will be requested from our clinical partners – Liverpool University Hospitals NHS Foundation Trust (LUFT) and Liverpool Clinical Laboratories (LCL).

15.5.3 Study population

The aim of this study is to generate a computer simulation model of adult patients with infection requiring broad-spectrum antimicrobial therapy. The collection of blood cultures from patients signifies sufficient clinician concern for sepsis, bloodstream infection or systemic infection. The collection of blood cultures is also often followed with empirical antimicrobial therapy. Therefore, blood culture requests will be used as an objective inclusion criterion for retrospective data inclusion into the study.

Inclusion criteria:

- Patients who were managed within a LUFT acute hospital site (Aintree or Royal) and had a concurrent blood culture investigation requested
- Age \geq 18 years at the time of the study

Exclusion criteria:

- Age $<$ 18 years at the time of the study
- Blood culture requested but patient not managed on an acute hospital site

Study period:

A 5-year period is targeted for the data collection.

One of the anticipated challenges is a significant change to the number and management of patients with bloodstream infection during the SARS-CoV-2 pandemic. Therefore, the study period must overlap this period of disruption (e.g., 2018 – 2023) in order to ensure that the model is not biased by the impact of the pandemic. Conversely, the pandemic's impact on the data presents a unique opportunity to ensure that the model is not overfit to the status quo data and that it can continue to make good predictions in periods of system stress. This will be achieved by a secondary analysis that filters the input parameter data as follows:

1. Patients treated before the onset of the SARS-CoV-2 pandemic (baseline)
2. Patients treated during and after the SARS-CoV-2 pandemic (comparator)

Other data not covered by the study population:

Additional data is required to complete non-direct patient care elements of the model. However, since these data can be reported in an aggregate manner, they are not considered part of the study population:

- Patients presenting to A&E triage (per hour)
- Ward staffing levels (per shift)

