15.5.4 Sampling

No sampling will be required, as all data within the study period will be included in the data analysis.

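### The comparator assigned to test prediction under system stress pools patients treated during and after the pandemic, so the stress signal may be diluted or confused

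*Protocol*

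**What the plan says.** Protocol section 15.5.3 sets the window for Sub-study 2: "A 5-year period is targeted for the data collection". It anticipates "a significant change to the number and management of patients with bloodstream infection during the SARS-CoV-2 pandemic", and so requires that "the study period must overlap this period of disruption (e.g., 2018 – 2023", the years being only an example.

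The section then gives the pandemic data a double use: to guard against a model overfitted to ordinary conditions, and to check that "it can continue to make good predictions in periods of system stress". The means is stated directly: "This will be achieved by a secondary analysis that filters the input parameter data as follows". Two filters follow:

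- baseline: "Patients treated before the onset of the SARS-CoV-2 pandemic (baseline"
- comparator: "Patients treated during and after the SARS-CoV-2 pandemic (comparator"

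No calendar date is given for the onset or the end of the pandemic, and there is no group for the pandemic alone or for the time after it. Section 15.5.4 adds: "No sampling will be required, as all data within the study period will be included in the data analysis".

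**The concern.** The protocol locates the disturbance in the pandemic, but the group assigned to show behaviour under disturbance runs from onset to the end of the window. Attendances, staffing, prescribing and culture requests may have differed between the disrupted months and what followed. If so, the comparator describes a mixture.

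Two misreadings become possible. A model that fails in the disrupted months could look adequate because later months offset the misfit. Conversely, a lasting change in practice after the pandemic could be read as an effect of stress. Section 15.3.2 intends the model to inform resource use and antimicrobial policy, so both behaviour under strain and fit to recent care matter. One pooled group does not show them separately.

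**Working it through.** The protocol gives no effect size, sample size or cut date for this comparison, so there is no figure to reproduce. The check has three parts.

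**1. The text.** In section 15.5.3 the change in numbers and management is attached to the pandemic period, the aim is prediction under stress, and the comparator is pandemic plus aftermath. Section 15.5.4 keeps all data in the window, so no later step removes the aftermath. The mismatch lies in what is stated and is not a detail left for an analysis plan.

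**2. How much the pooling could matter.** Let D be the true shift from baseline in a mean or proportion during disruption, D_after the shift in the later period, and f the share of comparator patients treated during disruption. Then

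pooled shift = f × D + (1 − f) × D_after.

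With a 5-year window, b years of baseline, s years of disruption and equal patient numbers per year, f = s / (5 − b).

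Only the 5 years comes from the protocol. Assumed: b from 1 to 2.5 years, s from 1 to 3 years, and equal yearly numbers. The last is a simplification, since the protocol itself expects numbers to change.

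For b = 2 the comparator lasts 5 − 2 = 3 years:

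| Disruption s (years) | f = s/3 | Share of D retained if D_after = 0 | Loss if D_after = 0 | Share of D retained if D_after = D/2, i.e. f + (1 − f)/2 |
|---|---|---|---|---|
| 1 | 0.33 | 33% | 67% | 67% |
| 1.5 | 0.50 | 50% | 50% | 75% |
| 2 | 0.67 | 67% | 33% | 83% |
| 2.5 | 0.83 | 83% | 17% | 92% |
| 3 | 1.00 | 100% | 0% | 100% |

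Over the whole assumed range:

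- Lowest share: b = 1, s = 1, so f = 1/4 = 0.25. With D_after = 0 the loss is 1 − 0.25 = 75%.
- Highest share: b = 2, s = 3, or b = 2.5, s = 2.5. Either gives f = 1.00, no post-pandemic time in the window and no loss.
- If pressure persisted in full (D_after = D), the pooled shift equals D whatever f is.
- If the later shift is larger than the shift under disruption (D_after > D), the pooled shift exceeds D, and a lasting change is read as stress.

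With separate strata, the during-versus-before contrast estimates D itself.

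**3. Why averaging matters for this kind of model.** The filter acts on input data, from which section 15.5.7 fits event rates and event times. Appendix 1 describes discrete event simulation as suited to queues, and delay in a queue is not linear in load. With assumed loads in the simplest single-server queue, mean wait in units of service time is ρ/(1 − ρ): 0.9/0.1 = 9 at 90% utilisation, 0.7/0.3 = 2.3 at 70%, and 0.8/0.2 = 4 at the averaged 80%. Inputs averaged over two regimes need describe neither of them. This shows the mechanism only and is no estimate for these hospitals.

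**The case against.** Four points can fairly be made for the plan.

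First, a reader might infer that the comparator *is* diluted by care free of stress. The protocol does not say that post-pandemic care returned to baseline. If pressure persisted, the pooled group could be largely a stress group. This stands, and it limits the point to a possibility.

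Second, a reader might infer that the problem holds however the comparison is run. That is not established. The text filters the input data and does not commit to one pooled summary. Table 5 in Appendix 3 keeps date-time fields for Sub-study 2, and the random date replacement in section 16.7 is described only for Sub-study 3. If simulated and observed outputs were set against calendar time within the comparator, a failure in the disrupted months could be seen. The protocol neither promises nor rules out such a display. This stands too, but it does not justify naming a mixed group as the stress comparator.

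Third, the split serves two aims. For the guard against overfitting to earlier conditions, everything after onset is a legitimate contrast with baseline. This stands, and the pooled contrast deserves to be kept for it.

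Fourth, a during/after split is not perfectly clean. It needs an end date that the protocol does not define, and the pandemic period may itself mix heavily and lightly disrupted months. This stands as a cost. Even so, whether the later period resembles baseline, stress or neither is an empirical question that three groups can answer and one pooled group cannot.

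**Conclusion.** The point holds in a limited form. Section 15.5.3 gives the stress test to a comparator that also contains post-pandemic patients, although it locates the disruption in the pandemic. If the two periods differ, the stress signal may be diluted or confused with a lasting change.

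The size cannot be determined from the documents. Under the assumed timings the disrupted share of the comparator lies between 0.25 and 1.00. The loss therefore runs from none to about 75% of the true shift, and the upper end also requires later care to equal baseline. Any single percentage would claim more than the protocol supports.

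This concerns one of two aims of a secondary analysis. The main deliverable, a parameterised and calibrated model, does not depend on it. It is a cheap improvement worth making, not a fault that undermines the study.

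**What to change.** In section 15.5.3, replace the two filters with three: before, during and after the pandemic. State the calendar dates of onset and end, with a short justification, and fix them before the data are opened.

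- Use the during period for the test of prediction under stress.
- Report the after period separately, as a check of fit to recent care.
- Keep the pooled post-onset contrast with baseline for the overfitting aim.

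No new data are needed, because the Sub-study 2 date-time fields in Table 5 allow each record to be assigned. The cost is one further filter, two dates in the text and fewer records in each period. The protocol gives no blood culture volumes, so the loss of precision cannot be stated; counts per period should be reported. The end date is a judgement, and repeating the analysis with one alternative date would show whether the conclusion depends on it.

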15.5.4 Sampling

No sampling will be required, as all data within the study period will be included in the data analysis.

15.5.5 Consent

This sub-study will require the processing of retrospective data collected for routine clinical care delivery. Identifiable data will be collected initially for the purpose of linking records across the multiple database sources. This data processing will be without collecting retrospective patient consent. Once data linkage has taken place, the data will be fully anonymised prior to any further processing and analysis.

15.5.6 Methods

The raw data for this project will be requested from our NHS partner organisation (LUFT and LCL), subject to their information governance requirements. At a high level, the following data will be required to create an accurate simulation of patients with bloodstream infection:

- Presentation of patients for acute care, such as the rate of patients presenting to A&E triage and the proportion of patients triaged with a sepsis diagnosis
- Clinical status (observations such as blood pressure, temperature, respiratory rate, etc.) of patients on presentation
- Laboratory investigation data – which patients had blood cultures collected and what where the results?
- Antimicrobial treatment and allergy history – what empirical antimicrobials were administered, if any, and was treatment modified later, e.g., with blood culture results
- Ward staffing data – in order to make accurate predictions of changes in staffing, the general staffing rates of wards must be known (nursing, physicians and auxiliary staff)
- Other patient characteristics, such as basic demographics (including age), main diagnosis, and co-morbidities
- Timings of events (e.g., time of blood culture collection, time of prescription of antimicrobials)

It is expected that the data will have to be pulled from multiple databases, including:

- Coding and admissions data
- Administrative data (e.g., patient ward transfers)
- Staffing data (e.g., ward nurse staffing)
- Prescribing data (e.g., antimicrobials)
- Laboratory data (e.g., blood culture analytical data)

The required data fields are all routinely collected for the delivery of clinical care.

A complete table of the data fields that will be collected is available in [Appendix 4 – Data collection fields](#).

15.5.7 Data analysis

Since data will be collected from disparate clinical databases, a data integration step is expected. This will be performed on the received pseudonymised data using Microsoft Excel, Microsoft Access and R (R Core Team, 2022). Records from different systems will be linked using a unique primary key (pseudonymous hash number generated by CIPHA system) in order to ensure referential integrity in later stages of data analysis. Details of the pseudonymised process can be found in section 16.7.

Data will then be analysed and summarised; the approach for this sub-study is to generate:

- 1) Descriptive data of patient characteristics and patient events (which will be utilised as covariates during analyses), e.g., patient observations, blood culture bacterial isolate, blood culture susceptibility, antimicrobial agent prescribed
- 2) Time based events fit to an appropriate probability distribution, e.g.:
 - a. Number of events per defined period of time – fit using a Poisson distribution, e.g., number of patients requiring empirical treatment for bloodstream infection per day/shift/hour
 - b. Time required for events to take place – fit using an exponential distribution, e.g., time take to administer prescribed antimicrobial, time taken for incubated blood culture to report positive

Probability distributions that have a closed form solution will be fit using maximum likelihood estimation. More complex models where a closed form solution is not possible or feasible will be fit using Bayesian estimation in the Stan modelling language (Stan Development Team, 2022).

Downstream to this point, data will be utilised both in aggregate form (e.g., proportions/probability, or probability distribution parameters) and using non-identifiable patient level (e.g., to create realistic simulated patients).

Data produced from this sub-study will be used to calibrate the simulation model. The model can be expressed with the following abstraction:

- 1) Parameter inputs within a parameter space – e.g., patient characteristics, staffing numbers, time required to perform blood culture investigation. Some parameters may be known with high certainty (e.g., incubation times for blood cultures) while others could be estimated but with residual uncertainty (e.g., time it takes for a clinician to perform a clinical review).
- 2) Model agent interactions – i.e., the simulation process itself
- 3) Output measurements – e.g., antimicrobial usage within the simulated population, time taken to administer effective antimicrobials (defined as first dose of antimicrobial to which the infecting organism is susceptible)

Given that certain input parameters are likely to be known only with low certainty, metaheuristic stochastic optimisation methods will be required to make informed estimates of these parameters and allow accurate simulation. These methods allow the estimation of parameters that cannot be differentiated, such as categorical variables or proportions. Examples of these methods include grid search, random search, hill climbing methods and genetic algorithms. Regardless of the optimisation method chosen, an objective function (e.g., a loss function of simulated output measurements and observed measurements) will be used to fit the model.

15.6 Sub-study 3 – Direct observation study

15.6.1 Aim

Produce detailed vertical observation data via direct patient observation to “fine tune” parameters that are otherwise insufficiently or inaccurately informed through retrospectively collected data.

15.6.2 Study setting

In order to maximise the data yield, the observational study will be performed on hospital areas expected to have the highest concentration of patients with suspected bloodstream infection and blood culture investigation requests:

- A&E
- Acute medical units

15.6.3 Study population

For the direct observation part of the study, blood culture requests are less suited as the sole primary inclusion criterion, since key events would have already occurred by the time the request is made.

This particularly applies to unwell patients with sepsis. The primary inclusion criterion for the observational study will therefore also include the point at which a positive sepsis screen is triggered.

Eligibility criteria:

- LUFT patients receiving hospital care in one of the study settings (A&E or acute medical units) during one of the observational study days
- Positive sepsis screen trigger (as defined by LUFT sepsis policy) AND/OR blood culture investigation request
- Age 18 years or above at the time of positive sepsis screen

Exclusion criteria:

- Age under 18 years at the time of sepsis screen or blood culture investigation request
- Patient no longer physically located within the study setting

15.6.4 Sampling

Where possible, all events relating to the management of patients in the study population within the study setting will be observed and recorded. It is acknowledged that this may not always be possible, for example if multiple patients satisfy the inclusion criteria but are being managed concurrently. In this case, the observer is allowed discretion to determine whether observation of the multiple events is possible.

15.6.5 Recruitment

Patients and staff will not be directly recruited for this sub-study. Prior approval will be sought from the ward manager.

15.6.6 Consent

This study is a non-interventional observational study with the main observation metrics being event times. Therefore, consent requirements are proportionate to the level of risk. Prior approval will be sought from the ward manager. Brief information on the nature of the study will be made available to staff at the daily handover, and informational posters will be made available on the wards. Although individual written informed consent will not be sought, the information material will indicate that an opt out system of consent will be in place. Prior to observing the delivery of direct patient care, the observer will introduce themselves to the patient as an observer for research purposes and allow for

the opportunity to opt out of the observations. On opting out, the observer will discontinue their direct observation of the staff member/s and/or patient/s.

15.6.7 Outcomes and objectives

The main deliverable of this sub-study is an adjunctive dataset collected through direct observation of patient management. Compared to the data generated by Sub-study 2, this data is expected to be on fewer patients but of high accuracy and resolution, likely to focus on time periods with comparatively high event concentration (e.g., first 4 hours of treatment). Being a prospective observational study, the data generated will:

- Validate the process flowcharts from Sub-study 1, and reveal any events that may have been missed
- Provide higher accuracy time requirements for individual events, since the retrospectively collected data from Sub-study 2 can have inaccurately recorded time-stamps

15.6.8 Methods

The study member or collaborator will observe the clinical management of patients being treated for suspected infection, and record the following in a bespoke database:

- Brief description of event (e.g., blood culture draw)
- Resource/s required for event (e.g., staff member, blood culture collection kit)
- Time taken for event (e.g., in minutes or hours)
- Outcome of event (e.g., successful or unsuccessful blood culture draw)

Direct observation of medical care provision generates the risk of performance bias, in particular the Hawthorne (observer) effect on the staff providing the care (Sedgwick and Greenwood, 2015). Where possible, observations will be conducted with minimal impact on staff and patients.

16 Ethical and regulatory consideration

